#### 9.3.7 Post-Trial Access to EPN-701

Not applicable.

#### 9.4 CONCOMITANT THERAPY

Concomitant therapy consists of any medication (e.g., prescription and over-the-counter drugs, vaccines, and nutritional supplements) used by a subject in addition to the study drug from the screening to the EOS/Early Termination visit. All such medications should be recorded on the Concomitant Medications eCRF.

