# 6.1.2 Long-Active Derivatives of Vitamin K2: Therapeutic role for Menaquinone-7

EPN-701 is a new formulation containing highly purified menaguinone-7 (MK-7) that belongs to the vitamin K2 family of compounds. Subject to approval by the FDA, EPN-701 would be the first and only drug approved for the orphan indication Calciphylaxis (also referred to as Calcific Uremic Arteriolopathy [CUA]), specifically to address peripheral soft tissue calcification and related calcification of the medial smooth muscle cells of the vasculature present in most ESRD patients. Menaguinones have a common functional naphthoguinone ring system (also shared with phylloquinone) and an unsaturated polyisoprenyl side chain. They are designated based on the length of the aliphatic side chains attached to the naphthoguinone ring (Booth and Suttie, 1998; Shearer and Newman, 2008). Menaquinone nomenclature is based on the number of isoprenoid units, and ranges from 1 to 15 (e.g., MK-7 for the vitamer with a side chain consisting of 7 isoprenoid units) (Marles et al. 2017). The chemical structure of MK-4 and MK-7 compared to phylloquinone (vitamin K1) is presented in Figure 4. Although both phylloquinones and menaguinones are fat-soluble, their lipophilicity increases substantially at increasing chain length. Thus, when compared to MK-4, MK-7 has high lipid solubility, greater tissue concentration and longer plasma half-life. While MK-7 and MK-4 are both well absorbed in humans, the plasma levels of MK-7 are significantly higher due to its longer half-life of 72 hours. In contrast, MK-4 has a half-life of approximately 3 hours (Schurgers and Vermeer, 2002; Schurgers et al. 2007c).

Dietary sources of menaquinones include chicken, egg yolk, dairy products, cow liver, and fermented foods such as cheese, yogurt, sauerkraut, and natto, a traditional Japanese food made from soybeans fermented with *Bacillus subtilis varnatto* (Schurgers et al. 2007c; Marles et al. 2017).

The naphthoquinone ring system shared by phylloquinones (vitamin K1) and menaquinones MK-4 and MK-7 (vitamin K2). The designation of MK-4 versus MK-7 is dependent upon the length of the aliphatic side chains attached to the naphthoquinone ring.

In addition, there are more than 200 dietary supplement products containing MK-7 currently on the market in the United States, the majority of which have a manufacturer's suggested MK-7 dose of 50 µg/d (NIH DSLD 2016). The Acceptable Daily Intake is 120 µg/day (FDA 2012).

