Vitamin K-dependent γ-carboxyglutamate proteins are synthesized in the liver, and help maintain normal blood coagulation through a balance of both procoagulant factors (II, VII, IX, and X) and anticoagulant proteins (C and S) (Schurgers et al. 2007c; Marles et al. 2017). Activated Protein C regulates the coagulation process by neutralizing the procoagulant activities of factors V and VIII in the presence of the cofactor Protein S (Marlar and Gausman, 2017). Hypercoagulable

states, such as protein C and/or protein S deficiencies have been reported in patients with calciphylaxis (the ultimate target population for EPN-701), and proposed as factors increasing the likelihood of calciphylaxis development (Wilmer and Magro, 2002; Nigwekar et al. 2008).

In a randomized study evaluating the effect of vitamin K2 supplementation on functional vitamin K deficiency in adult hemodialysis patients, patients on hemodialysis (N=53) had 4.5-fold higher dp-ucMGP and 8.4-fold higher uncarboxylated osteocalcin levels compared with healthy agematched controls (N=50). PIVKA-II levels were elevated in 49 hemodialysis patients. Vitamin K2 supplementation induced a dose- and time-dependent decrease in circulating dp-ucMGP, uncarboxylated osteocalcin, and PIVKA-II levels. Response rates in the reduction in dp-ucMGP levels were 77% and 93% in the groups receiving 135 µg and 360 µg of menaquinone-7, respectively (Westenfeld et al. 2012). The results of this study provide a rationale for the use of plasma PIVKA-II, MGP, and osteocalcin as biomarkers in an interventional clinical trial of vitamin K supplementation in hemodialysis patients.

Fetuin A has been characterized as a critical regulator of calcification in humans, and as such is of interest to monitor in interventions targeting calcification (Jahnen-Dechent et al., 2011). Likewise, osteoprotegerin is also thought to be a regulator of calcification, making it of interest here (Price et al., 2001). Finally, the T-50 test has been shown to correlate strongly with the propensity of blood to form calcifications, wherein a short T-50 is indicative of blood likely to form calcifications, and a lengthening of T50 for patients at risk would be desireable (Pasch et al., 2017).

Hs-CRP is widely acknowledged to be indicative of inflammations of various kinds and if elevated, can signal inflammatory events prior to clinical symptoms.

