### Secondary Objectives:

- To determine, in subjects with ESRD on stable hemodialysis, the plasma levels of the following biomarkers after two weeks of EPN-701 treatment relative to baseline:
  - Uncarboxylated MGP
  - Uncarboxylated osteocalcin
  - Activated Protein C
  - o PIVKA-II.

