#### 9.1.2 Exclusion Criteria

Subjects meeting any of the following exclusion criteria will be excluded from the study:

- 1. Chronic kidney disease not requiring hemodialysis
- 2. Acute kidney injury treated with hemodialysis
- 3. Diagnosis of confirmed calciphylaxis
- 4. History of any solid organ transplant
- 5. History of malignancy within 2 years of study enrollment, except for adequately treated carcinoma *in situ* of the cervix and non-melanoma skin carcinoma.

- 6. History of any major surgery (defined as a surgical procedure involving the cranium, chest, abdomen, or pelvic cavity, or other procedure performed under general anesthesia) within 1 month prior to the first dose of study drug. Subjects with a recent (within <1 month) revision and/or placement of arteriovenous fistula (AVF) will be allowed to participate.
- 7. History of a major cardiovascular event (such as cerebrovascular accident [CVA], transient ischemic attack [TIA], myocardial infarction, unstable angina) within 1 month prior to the first dose of study drug.
- 8. Any co-existing disease or condition that may compromise the safety of study participants and/or the integrity of the study, including, but not limited to:
  - o Class C or Class D Cirrhosis of the liver
  - Known intestinal malabsorption
  - Inability to take oral medication
- 9. Life-expectancy <3 months
- 10. Known history or positive serology for Human Immunodeficiency Virus (HIV), positive serologies of E antigen or with polymerase chain reaction (PCR) positive titers for hepatitis B virus (HBV). Subjects with positive serologies for hepatitis C but with negative PCR for active virus will be allowed.
- 11. Severe infection requiring intravenous (IV) antibiotics within two weeks prior to the first dose of study drug.
- 12. Warfarin taken within two weeks prior to the first dose of study drug. Subcutaneous heparin, enoxaparin and novel oral anticoagulants (NOAC; such as apixaban) are permitted.
- 13. Treatment with an investigational drug within four weeks prior to the first dose of study drug.
- 14. Pregnancy or lactation.
- 15. Any other disease or condition which, in the judgment of the Investigator, would place a subject at undue risk by being enrolled in the trial, or cause inability to comply with the trial.

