# 9.4.1 **Prohibited Therapy**

Patients receiving long-term warfarin (Coumadin) frequently develop asymptomatic excessive prolongation of their international normalized ratio (INR) results. The anticoagulant effect of warfarin, functioning by its interference with the clotting effect of vitamin K, can be offset with as little as 1 mg of vitamin K (Crowther et al. 1998). Therefore, use of vitamin K is contraindicated in individuals on warfarin therapy (Vitamin K2 Monograph, 2009).

Medications that are prohibited while the subject is receiving study drug are listed in Table 3.

Table 3 Washout Periods for Prohibited Medications

Prohibited Medication	Minimum Washout Period Prior to the First Dose of Study Drug
Any investigational therapy	4 weeks
Warfarin*	2 weeks
IV antibiotics	2 weeks
Prescription and non-prescription medications known to be sensitive substrates of CYP3A** or CYP4F2***	None
Herbal and homeopathic remedies	None

Abbreviations: IV=intravenous

The investigator should contact the Medical Monitor if questions arise regarding medications not listed above.

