#### 9.4.2 Prohibited Food

No foods are prohibited during treatment with the study drug.

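### Vitamin K and MK-7 supplements are recorded but not restricted, so a subject can enrol with a partly treated Day 1 baseline and the single-arm changes in three secondary biomarkers can be understated

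*Combined protocol and SAP*

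**What the plan says.** Section 9.4 counts as concomitant therapy any medication ("prescription and over-the-counter drugs, vaccines, and nutritional supplements) used by a subject in addition to the study drug") between screening and the end-of-study visit. Its only instruction is to enter these on the eCRF. Section 9.6.3 adds a 30-day medication history before first dose, including over-the-counter products.

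Restrictions are found in two places. Among the 15 exclusion criteria in Section 9.1.2, the only one touching the vitamin K pathway is criterion 12: "Warfarin taken within two weeks prior to the first dose of study drug". Section 9.4.1 then states: "Medications that are prohibited while the subject is receiving study drug are listed in Table 3". That table has five rows: investigational therapy, warfarin, IV antibiotics, sensitive CYP3A or CYP4F2 substrates, and "Herbal and homeopathic remedies". The last row carries no washout. Vitamin K is named in neither place. Section 9.4.2 adds: "No foods are prohibited during treatment with the study drug".

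The background sections show why supplements are relevant. Section 6.1.2 says that "there are more than 200 dietary supplement products containing MK-7 currently on the market in the United States", most with a suggested dose of 50 µg/day. Section 6.3.3 reports from a randomized trial in hemodialysis patients: "Response rates in the reduction in dp-ucMGP levels were 77% and 93% in the groups receiving" 135 µg and 360 µg of MK-7.

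The secondary objective in Section 7 is to determine "the plasma levels of the following biomarkers after two weeks of EPN-701 treatment relative to baseline". Section 11.8 summarises changes at Day 15 and Day 22. Section 11.4 takes the last pre-dose value as baseline, and Section 11.9 plans no subgroup analyses.

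**The concern.** The plan removes subjects taking the vitamin K antagonist but is silent on subjects taking vitamin K itself, including the molecule under test. A site that applies Sections 9.1.2 and 9.4.1 as written has no stated reason to refuse a daily MK-7 user.

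For such a subject the Day 1 value may already reflect MK-7 exposure, leaving less room for EPN-701 to lower the marker. The study has one arm, so no concurrent control shares the problem, and Section 11 neither separates nor adjusts for prior use. Starting or stopping a supplement between Day 1 and Day 22 would likewise move a marker for a reason other than EPN-701.

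What is at stake is the secondary biomarker description. Section 6.3.1 says that the planned Phase 2b trial will ask whether EPN-701 can normalize calcium-chelating proteins, and these would be the sponsor's first biomarker data on EPN-701 bearing on that question.

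**Working it through.** The plan has no figure to reproduce: Section 11.2 states that no sample size calculation was made, and all analyses are descriptive. The check is a reading of the restrictions, followed by an illustration of size.

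**1. Could an existing rule already cover supplements?**

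- The herbal and homeopathic row of Table 3 and Section 9.4.1.1 do not name vitamins or nutritional supplements. Even on a broad reading, the row requires no washout, so a treated baseline would remain possible.
- Section 9.4.1 calls vitamin K contraindicated, but for people on warfarin. It is the reason for barring warfarin and does not restrict vitamin K in this study.
- The CYP4F2 row gives fingolimod as its example. Nothing in the documents calls MK-7 a sensitive CYP4F2 substrate.
- Section 9.6.3 has contraindicated medications stopped or replaced, but refers back to Section 9.4.1, which does not list vitamin K.
- Table 3 applies while study drug is being taken. Table 1 has dosing from Day 1 through Day 14, so even a listed item would not clearly be covered at the Day 22 sample.

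**2. Which endpoints have documentary support for an effect?** Section 6.3.3 reports dose- and time-dependent falls in dp-ucMGP, uncarboxylated osteocalcin and PIVKA-II with MK-7. It gives no MK-7 response for Activated Protein C. The support therefore covers three of the four secondary biomarkers.

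**3. Size of the dilution.** Inputs: n = 15 (Section 11.2) and an assumed true fall of 50%. Section 6.3.2 ties a figure of about 50% for uncarboxylated MGP to 1.0 mg of MK-7, not to 10 mg for 14 days, so it serves here only as a working value. Let m be the number of users and r the fall that a user shows.

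Mean fall = [50 × (15 − m) + r × m] / 15

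| Users m | r = 25% (half the fall) | r = 0 (no further fall) |
|---|---|---|
| 1 | (700 + 25)/15 = 48.3% | 700/15 = 46.7% |
| 2 | (650 + 50)/15 = 46.7% | 650/15 = 43.3% |
| 3 | (600 + 75)/15 = 45.0% | 600/15 = 40.0% |

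**4. Chance that any user enrols.** Prevalence is not in the documents. If it were p, the chance of at least one user among 15 is 1 − (1 − p)^15. For assumed values of 5%, 10% and 20% this gives 54%, 79% and 96.5%.

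**5. Does the screening window clear MK-7?** The stated half-lives are 72 h (Section 6.1.2) and 68 h (Section 6.2.3). Fraction remaining = 0.5^(t / half-life). For t = 7 days = 168 h:

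- 72 h: 168/72 = 2.33 half-lives, 19.8% remaining
- 68 h: 168/68 = 2.47 half-lives, 18.0% remaining

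A subject who stops on the first day of screening would still carry about 18–20% of the earlier plasma level on Day 1. This concerns plasma MK-7 only. The documents do not say how fast the carboxylation markers return to untreated levels.

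**The case against.** The strongest reply is that the gap may have little effect. Section 6.1.2 puts most products at 50 µg/day, whereas the response rates quoted in Section 6.3.3 start at 135 µg. The study dose is 10,000/50 = 200 times the usual supplement dose, and the cited response is dose-dependent, so a user could still show most of the fall. A response rate at a low dose also does not show that no further response is possible. All of this stands, and it makes the no-further-fall column an extreme bound.

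Use would also be traceable. The 30-day history and later changes are recorded, concomitant medications are listed by subject (Section 11.6.2), and medians and ranges accompany the means. The pre-dose Day 1 PK sample might reveal earlier MK-7 exposure. Questions about unlisted medications go to the Medical Monitor, and exclusion criteria 8 and 15 leave room for judgement. These provisions help identify a user afterwards or allow a decision case by case. None names vitamin K, and no planned analysis uses the information.

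Finally, this is a 15-subject safety study whose primary endpoint is treatment-emergent adverse events. That stands as well and limits the weight of the point.

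A reader might infer that the secondary biomarker results are diluted, and for all four markers. The documents do not support that. They do not show that any user will enrol, they report no response at 50 µg/day, and they give no MK-7 response for Activated Protein C.

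**Conclusion.** The omission is certain from the text; its effect is conditional. If MK-7 users enrol and their markers already respond at supplement doses, the changes from baseline in uncarboxylated MGP, uncarboxylated osteocalcin and PIVKA-II would be understated, and nothing in the design or analysis would separate them.

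On the assumed 50% true fall, one to three users among 15 would lower the mean by 1.7 to 5.0 percentage points if they show half the fall, and by 3.3 to 10.0 points at the extreme bound. Those figures rest on an effect size borrowed from a different dose, on assumed numbers of users and on assumed residual responses. They show scale and are not a forecast.

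The primary safety endpoint is not directly affected. Because the analyses are descriptive, no error rate or power figure changes. The point is worth acting on because the remedy is cheap and the ingredient at issue is the study drug's own.

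**What to change.** 1. In Section 9.1.2, the synopsis and Table 3, state explicitly how use of vitamin K-containing supplements is handled before and during the study, and extend that statement through the Day 22 biomarker sample. The sponsor should set and justify the look-back. Two facts bear on it: Section 9.6.3 already collects a 30-day history, and the seven-day screening window alone leaves about 18–20% of plasma MK-7. The justification should also address marker recovery, which plasma half-life does not settle. Since food is unrestricted, the aim is a baseline free of supplements, not one free of vitamin K.
2. Have the 30-day history and the concomitant medication record ask specifically about vitamin K-containing supplements.
3. In Section 11.8, prespecify that biomarker changes at Day 15 and Day 22 are summarised with and without any subject who has recorded vitamin K supplement use.

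The cost is protocol and eCRF wording plus one additional summary table. There may be a few more screen failures; how many cannot be judged, because the documents give no prevalence of use.

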# 9.4.1 **Prohibited Therapy**

Patients receiving long-term warfarin (Coumadin) frequently develop asymptomatic excessive prolongation of their international normalized ratio (INR) results. The anticoagulant effect of warfarin, functioning by its interference with the clotting effect of vitamin K, can be offset with as little as 1 mg of vitamin K (Crowther et al. 1998). Therefore, use of vitamin K is contraindicated in individuals on warfarin therapy (Vitamin K2 Monograph, 2009).

Medications that are prohibited while the subject is receiving study drug are listed in Table 3.

Table 3 Washout Periods for Prohibited Medications

Prohibited Medication	Minimum Washout Period Prior to the First Dose of Study Drug
Any investigational therapy	4 weeks
Warfarin*	2 weeks
IV antibiotics	2 weeks
Prescription and non-prescription medications known to be sensitive substrates of CYP3A** or CYP4F2***	None
Herbal and homeopathic remedies	None

Abbreviations: IV=intravenous

The investigator should contact the Medical Monitor if questions arise regarding medications not listed above.

#### 9.4.1.1 Herbal Therapies

The use of herbal therapies will be prohibited during the study.

#### 9.4.2 Prohibited Food

No foods are prohibited during treatment with the study drug.

#### 9.5 STUDY VISITS

The schedule of assessments to be performed during the study is provided in **Table 1**. All activities must be performed and documented for each subject.

\* Subcutaneous heparin, enoxaparin and novel oral anticoagulants (NOAC; such as apixaban) are permitted.

\*\* As listed in the FDA *Drug Development and Drug Interactions: Table of Substrates, Inhibitors and Inducers* (2017)

\*\*\* Example: fingolimod

The expected duration of study participation for an individual subject is approximately five weeks, including up to one week for screening, two weeks of study treatment, and two weeks of post-treatment safety follow-up.

Subjects will undergo a total of 14 visits during their study participation: Screening visit (within seven days prior to the first dose of study drug), three visits per week during the two-week treatment, and two-week safety follow-up periods (coinciding with the subject's hemodialysis schedule), and the EOS/Early Termination visit. Baseline assessments will be completed prior to the first study drug intake on Day 1. The EOS/Early Termination visit will occur two weeks after the last dose of study drug (on study Day 29).

Subjects will be closely monitored for safety and tolerability throughout the study. At each treatment visit, assessments should be completed prior to the study drug administration, unless otherwise stated.

At each study visit, subjects will also undergo hemodialysis, as per their standard ESRD management; hemodialysis is therefore not listed as a study-related assessment in the following sections.

# 9.5.1 Screening Visit (Day -7 to Day -1)

Subjects will undergo the following assessments during screening:

- Obtaining informed consent and Health Insurance Portability and Accountability Act (HIPAA) authorization (see Section 9.6.1 for details)
- Review of eligibility (inclusion and exclusion) criteria (see Sections 9.1.1 and 9.1.2 for details)
- Recording of general medical history (including menstrual history for females of childbearing potential), disease history, and demographics (see Section 9.6.2 for details)
- Recording of baseline and concomitant medications (see Section 9.6.3 for details)
- Complete physical examination, measurement of height and weight (see Section 9.6.4 for details)
- Standard 12-lead ECG within 60 minutes pre-dialysis (see Section 9.6.6 for details)
- Measurement of vital signs (blood pressure, heart rate, respiratory rate, and oral body temperature (pre-dialysis) (see Section 9.6.5 for details)
- Testing for HIV, hepatitis B and C (see Section 9.6.8.1 for details)
- Collection of blood samples for safety laboratory tests pre-dialysis (hematology, CMP, coagulation panel, and serum β-hCG pregnancy test (females of childbearing potential only) (see Section 9.6.8.1 for details).

# 9.5.2 Visit 1 (Day 1, Baseline), Visit 4 (Day 8), Visit 7 (Day 15, End-of-Treatment), and Visit 10 (Day 22) [Mondays]

Subjects will undergo the following assessments during these visits:

- (At baseline/Visit 1 only:) Review of eligibility (inclusion and exclusion) criteria (see Sections 9.1.1 and 9.1.2 for details)
- Recording of any changes in concomitant medications (see Section 9.6.3 for details)
- (At Visit 7 only, if clinically indicated:) Symptom-driven physical examination (see Section 9.6.4 for details)
- (At Visits 1, 4, and 7): Measurement of body weight within 60 minutes pre-dialysis and within 60 minutes post-dialysis (see Section 9.6.4 for details)
- (At Visit 7 only): Standard 12-lead ECG within 60 minutes pre-dialysis (see Section 9.6.6 for details)
- (At Visits 1, 4, and 7): Measurement of vital signs (blood pressure, heart rate, respiratory rate, and oral body temperature within 30 minutes pre-dialysis and within 30 minutes post-dialysis (see Section 9.6.5 for details)
- Collection of blood samples for safety laboratory tests pre-dialysis (hematology, CMP, coagulation panel) (see Section 9.6.8.1 for details)
- (At Visits 1, 7, and 10): Collection of blood samples for biomarker assessments pre-dialysis (pre-dose) (see Section 9.6.8.2 for details):
  - o MGP, osteocalcin, Protein C, PIVKA-II protein, Fetuin A, osteoprotegerin, *hs*-CRP, and Time to Formation of Secondary Calciprotein Particles (T-50 Test); including CPP size.
- Collection of blood samples for PK assessments pre-dialysis/pre-dose (at the time of needle placement) (Visits 1, 4, and 7), during dialysis (Visits 1 and 4) and at the end of dialysis (before needle removal) (Visits 1, 4 and 7) (see Section 9.6.8.3 for details)
- (At Visits 1 and 4 only): Study drug administration pre-dialysis (immediately after needle placement and the pre-dialysis biomarker sampling) (see Section 9.3.5 for details)
- Recording of changes in baseline complaints under general medical history (events occurring before the first dose of study drug [Visit 1 only]; see Section 9.6.2 for details) or AEs (events occurring after the first dose of study drug [Visit 1 post-dose and subsequent visits]; see Section 10.3 for details). Any occurrence of dialyzer clotting (assessed at each dialysis session) is to be recorded as an AE (see Section 10.3.2).
- Kt/V will be calculated at baseline as the average of the last three pre-study Kt/V values obtained as part of the subject's standard of care. At Visit 7, Kt/V will be measured and compared with the baseline value.

Assessments completed after the last dose of study drug on study Day 15/Visit 7 (or earlier in case of an early discontinuation of the study treatment) will be considered EOT assessments.

At the end of Visit 1, subjects will receive a sufficient supply of the study drug for two weeks of treatment.

